## **Adoptability**

Rates of enrollment are reported descriptively but not analyzed between groups, as enrollment occurred prior to group assignment.

## **Feasibility**

We investigated differences across groups (in-person versus telehealth) in whether the first visit occurred within 1 week of NICU discharge, average number of days between NICU discharge until first Baby Bridge visit, frequency of visits, number of therapy visit cancellations, and the completion rates using independent samples t-tests and chi-square analysis.

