## Study Protocol and Statistical Analysis Plan

### **Participants and setting**

Participants included 20 high-risk parent-infant dyads hospitalized in an urban, level IV NICU. Consecutively eligible dyads from May 2023 to April 2024 were recruited if the infant was hospitalized in the NICU for > 7 days; received a referral for post-NICU physical therapy, occupational therapy, and/or speech-language pathology (or for the state-wide early intervention program) at NICU discharge; was referred to the Baby Bridge program at least 48 hours before NICU discharge; had a chronological age of < 6 months at the time of NICU discharge; and were from a family who spoke English. Infants who lived any distance away from the hospital were enrolled; however, infants who were not going to reside in the state of California following NICU discharge were excluded. Infants were deemed 'high-risk' for developmental challenges if they were recommended by the NICU medical team for therapy. Although we acknowledge that the term "high risk" can refer to high risk of medical complications or high risk of cerebral palsy, we use the term "high risk" to define the infant's need for therapeutic interventions across a multitude of constructs including for language, cognition, self-regulation, sensory, motor, and feeding. A member of the research team attended weekly discharge rounds and reviewed the electronic medical record. Within discharge rounds, communication between the medical team and research team occurred, and the medical team referred infants to the Baby Bridge program through an online referral process in REDCap. The research team then screened and recruited those who were eligible.

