Enrolled infants and families were randomized to receive Baby Bridge services either through telehealth or in-person visits. Parent-infant dyads were enrolled at least 2 days before NICU discharge to enable rapport to be established (between the Baby Bridge therapist and family) through a visit to the NICU when possible and via telephone, text or email messaging when an in-person visit was not possible prior to discharge. This first contact was attempted to be in-person in the NICU for both the telehealth and in-person groups. Enrolled infants and families then had a Baby Bridge telehealth or in-person visit scheduled within one week of discharge (depending on their group assignment). Subsequent individual weekly visits were adapted to in-person or telehealth (varying from assigned group) when needed or deemed appropriate (requested by the family or therapist or when an in-person visit was felt to improve the quality of the therapy session). Weekly Baby Bridge programming was conducted until other therapy through the state-wide early intervention program commenced, as in the infant was receiving therapy services as recommended. We also tracked rates of enrollment, rates and reasons for any cancellations, and completion of the program (defined as being seen until community-based early intervention services commenced). Infants were withdrawn if they were transferred to another hospital or if they were readmitted to the hospital and additional contact was not possible or feasible.

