### ***Feasibility***

Feasibility is defined as the extent to which Baby Bridge programming can be successfully used or carried out within a given agency or setting (Proctor et al., 2011). To understand the feasibility of Baby Bridge telehealth programming, we captured timing (if the first visit was conducted within one week of discharge); average time from NICU discharge to first Baby Bridge visit); frequency of visits; rate and reasons for any therapy visit cancellations; the completion rates (percentage of enrolled infants who completed programming); and the timing of transition to community-based therapy. Feasibility was defined a priori as all Baby Bridge visits attempted within the first week, infants seen at least 3 visits per month while in the program, and that 80% would be successfully transitioned to early intervention programming.

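### Mean days to first visit can be compared only among infants who were visited, so an arm that missed its slowest infants could look faster; the plan needs a rule for infants with no visit

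*Combined protocol and SAP*

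**What the plan says.** Under Implementation outcomes, Feasibility, one of the timing measures is the "average time from NICU discharge to first Baby Bridge visit". Under Analysis, Feasibility, the in-person and telehealth groups are compared on "average number of days between NICU discharge until first Baby Bridge visit" and on "whether the first visit occurred within 1 week of NICU discharge", "using independent samples t-tests and chi-square analysis". The t-test must be meant for the mean and the chi-square for the yes/no outcome. Neither section says how an infant with no first visit is handled, what the denominator of the 1-week proportion is, or which infants form the analysis population.

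Participants and setting supplies the rest:

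- Size: "Participants included 20 high-risk parent-infant dyads hospitalized in an urban, level IV NICU".
- Allocation: "Enrolled infants and families were randomized to receive Baby Bridge services either through telehealth or in-person visits". No ratio is given.
- Timing of entry: "Parent-infant dyads were enrolled at least 2 days before NICU discharge".
- Withdrawal: "Infants were withdrawn if they were transferred to another hospital or if they were readmitted to the hospital". The sentence goes on to add a condition that further contact could not be had. Readmission alone therefore does not remove an infant.

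**The concern.** A day count exists only once a visit has taken place. The type of first visit depends on the assigned group, so allocation comes before the first post-discharge visit, and an infant lost in between is randomised but has no value. A t-test on days then compares the infants reached in one arm with the infants reached in the other. If those not reached would have been the late ones, their arm's mean falls because the programme failed to see them, while an arm that does see such infants late is penalised.

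Prompt contact after discharge is central to a bridging programme, and the pilot is meant to inform a larger trial. A mean that can improve when infants are missed is a poor basis for that.

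**Working it through.** **Plan's own figure.** There is none to reproduce. The plan states no power, standard deviation or expected number of days, and gives no count of infants without a visit. Every value below other than the total of 20 dyads is an assumption, including 10 per arm.

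**1. Worked example.** In both arms, eight infants are first seen on days 3, 4, 4, 5, 5, 6, 6 and 7. In arm A the other two are never seen. In arm B they are seen on days 18 and 24.

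- Arm A mean, infants visited: (3+4+4+5+5+6+6+7)/8 = 40/8 = 5.0 days.
- Arm B mean: (40+18+24)/10 = 82/10 = 8.2 days.
- Difference: 8.2 − 5.0 = 3.2 days in favour of the arm that reached fewer infants.
- Pooled t-test: p = 0.22.
- Exact rank-sum test with the two never-visited infants ranked last: rank sums 107 (A) and 103 (B) against an expected 105, p = 0.91. Arm A no longer looks faster.
- Seen within 7 days, all randomised infants in the denominator: 8/10 in both arms. Visited infants only: 8/8 = 100% in A and 8/10 = 80% in B. The 1-week outcome is thus protected only if its denominator is fixed.

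**2. Simulation when the slowest infants are missed.** Time to first visit is T = 6 × exp(s × Z), with Z standard normal. This gives a median of 6 days, the same in both arms. There are 10 per arm and 50,000 trials per row. In one arm the k slowest infants are never visited, and the planned comparison is run on those left.

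| s | k missed | Apparent advantage (days) | Trials in which that arm looks faster | p < 0.05 in its favour |
|---|---|---|---|---|
| 0.6 | 0 | 0.0 | 50.3% | 2.2% |
| 0.6 | 1 | 1.0 | 69.7% | 5.5% |
| 0.6 | 2 | 1.6 | 81.7% | 9.9% |
| 0.6 | 3 | 2.2 | 89.4% | 14.0% |
| 0.4 | 1 | 0.5 | 68.2% | 6.1% |
| 0.4 | 3 | 1.3 | 87.8% | 15.7% |
| 0.8 | 1 | 1.6 | 71.0% | 5.2% |
| 0.8 | 3 | 3.4 | 90.7% | 12.1% |

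If the arm with missed infants is truly 20% slower (s = 0.6), it still looks faster in 44.9%, 60.5% and 72.8% of trials with 1, 2 and 3 missed.

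**3. Simulation when the loss is random.** With 2 or 3 infants lost at random (s = 0.6), the mean difference is 0.00 or −0.01 days, and the arm looks faster in 50.8% or 51.4% of trials. There is no systematic shift.

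**The case against.** The case against is substantial.

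- **No affected infant is documented.** The exclusion is inferred from the plan's silence. If every infant was visited, the selection problem does not arise. This stands.
- **Delivery mode is not shown to drive loss.** A reader might infer that being reached is itself an effect of telehealth or home visiting. The documents do not support that. The only stated routes to withdrawal are transfer, and readmission with contact no longer achievable, and nothing links either to mode. In-person visits could also be moved to telehealth for reasons such as distance or therapist scheduling, which narrows the scope for mode-driven failure. What remains is that reach may differ by arm, if only by chance in groups this small.
- **Other outcomes help.** Completion is a percentage of enrolled infants, so a never-visited infant counts as a non-completer there, and the 1-week proportion is read beside the mean. This stands in part: completion does not single out infants with no first visit, and the 1-week denominator is unstated.
- **The example is extreme.** Days 18 and 24 are invented, although first visits were to be scheduled within a week, and the t-test there gives p = 0.22. The example shows the direction of the distortion in the descriptive means, not a false positive.
- **Ranking every never-visited infant last is crude.** It puts an early readmission below a day-24 visit and so treats a medical event as a programme failure. This stands, and is why the fix includes a sensitivity analysis.

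**Conclusion.** The point holds as a conditional one. As planned, the comparison of mean days can use only visited infants. If any randomised infant had no visit, it conditions on an event after randomisation, and an arm that missed its slowest infants can look faster. Under the assumptions above, one missed infant shifts the mean by 0.5 to 1.6 days and three by 1.3 to 3.4 days. That needs the missed infants to be those who would have been seen late.

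It would go too far to read this as showing that the trial's day comparison is biased, since the number never visited and its split by arm are not given. Nor does it touch the primary outcome: cost is analysed by actual visit type. Average days is also not among the a priori feasibility criteria, which use attempted first-week visits, visits per month and transition to early intervention. For a secondary feasibility outcome in an unpowered 20-dyad pilot, the point is minor to moderate: worth changing, not critical.

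**What to change.** In Analysis, Feasibility, for all randomised infants discharged from the NICU to home:

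1. Report by arm the number never visited, with the reason. Count infants transferred before discharge separately.
2. Analyse the proportion first visited within 7 days, keeping never-visited infants in the denominator as not met.
3. Show time from discharge to first visit as cumulative incidence by arm, with readmission or withdrawal before any visit as a competing event.
4. Compare arms by an exact rank-sum test with never-visited infants ranked last. Add a sensitivity analysis that excludes or censors infants readmitted before any visit.
5. Label any mean that is kept as applying to infants visited.

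The planned mean already needs the discharge and visit dates. The added need is the date and reason of any readmission or withdrawal before a first visit. The cost is slightly more analysis, and a headline that is no longer a simple mean. If no infant was missed, one sentence saying so settles the selection question.

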### ***Adaptations***

Adaptations include intentional changes made to programming (from the way it was intended) in order to enable real-world uptake by aligning the intervention to the context it exists in (Moore et al., 2021). To aid in understanding specific adaptations made to telehealth versus in-person programming, we captured the proportion of visits conducted via telehealth in the telehealth group and proportion of visits that occurred in-person in the in-person group. Reasoning for such adaptations was tracked as described above in the telehealth and in-person assignment sections.

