## **Analysis**

A power analysis to determine sample size was not conducted, as this is a pilot study aimed at understanding initial differences across groups while determining variance to aid in future sample size determination for a larger trial. Sociodemographic and medical factors are reported descriptively and differences across groups were investigated using independent samples t-tests and chi-square analysis.

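### Cancellations are recorded as a rate but compared between arms as a number with no denominator, although time in the programme varies by infant

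*Combined protocol and SAP*

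**What the plan says.** Two places describe the measure as a rate. Participants and setting says the study tracked "rates and reasons for any cancellations", and the Feasibility entry under Implementation outcomes lists "rate and reasons for any therapy visit cancellations". Neither names a denominator.

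The Feasibility paragraph of the Analysis section then lists what is compared between arms, including "frequency of visits, number of therapy visit cancellations, and the completion rates". It names independent samples t-tests and chi-square for five outcomes together and does not say which test goes with which outcome. No offset or adjustment for length appears there or elsewhere.

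Time in the programme is not fixed. Participants and setting says "Weekly Baby Bridge programming was conducted until other therapy through the state-wide early intervention program commenced", and also that "Infants were withdrawn if they were transferred to another hospital" (or were readmitted and further contact was not possible or feasible).

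**The concern.** An infant who waits longer for early intervention has more visits available to cancel. A count without a denominator therefore reflects both the tendency to cancel and the time at risk. Two things follow.

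- **Precision.** Variation in length adds noise to the count, even when length is balanced between arms.
- **Distortion.** If length differs by arm, equal cancellation rates can look different and different rates can look equal.

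The plan standardises for exposure elsewhere. One feasibility criterion is "infants seen at least 3 visits per month while in the program". For adaptations, "we captured the proportion of visits conducted via telehealth in the telehealth group", and the Analysis section compares that proportion by t-test. Cancellations are the exception.

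This bears on the pilot's stated purpose of "determining variance to aid in future sample size determination for a larger trial": the variance of a count includes the variance of programme length.

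**Working it through.** There is no figure in the plan to reproduce: it states no cancellation rate, programme length, effect size or power. The textual points are settled by reading: a rate in two places, a number in the analysis, and open-ended length. What follows illustrates the consequence.

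**From the documents:** 20 dyads in two randomised arms.

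**Assumed:** 10 per arm; two-sided 5%; lognormal scheduled visits, rounded, minimum 1; log-SD 0.7 (wide) or 0.3 (narrow); binomial cancellations, with between-infant intraclass correlation ρ of 0 or 0.1.

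**1. Expected count.** This is the cancellation probability times scheduled visits. At 20%, 4 visits give 0.2 × 4 = 0.8 and 24 visits give 0.2 × 24 = 4.8, a six-fold spread from length alone.

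**2. Share of count variance due to length.** With n scheduled visits of mean m,

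Var(count) = p(1−p)[m + ρ(E(n²) − m)] + p²Var(n).

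Take p = 0.2 and m = 10.
- Log-SD 0.7: Var(n) = 100(e^0.49 − 1) = 63.2, so the length term is 0.04 × 63.2 = 2.53. The other term is 0.16 × 10 = 1.60 at ρ = 0, or 0.16 × (10 + 0.1 × 153.2) = 4.05 at ρ = 0.1. The shares are 2.53/4.13 = 0.61 and 2.53/6.58 = 0.38.
- Log-SD 0.3: Var(n) = 9.42, and the shares are 0.19 and 0.11.

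**3. Simulation.** 20,000 trials per scenario, percentage rejecting. Ranges span ρ = 0 and ρ = 0.1.

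| Log-SD | True rates | Mean visits | t-test on counts | t-test on per-infant rate |
|---|---|---|---|---|
| 0.7 | 20% v 20% | 10 v 10 | 3.9–4.4 | 4.7 |
| 0.7 | 20% v 20% | 10 v 12 | 5.0–6.0 | 4.8 |
| 0.7 | 20% v 20% | 8 v 16 | 17.9–28.9 | 5.1–5.6 |
| 0.3 | 20% v 20% | 8 v 16 | about 31–58 | about 5 |
| 0.7 | 10% v 20% | 16 v 8 | 4–5 | 20–29 |
| 0.3 | 10% v 20% | 16 v 8 | 4–5 | 25–42 |
| 0.7 | 10% v 25% | 10 v 10 | 30.0–40.3 | 42.2–58.2 |
| 0.3 | 10% v 25% | 10 v 10 | 45.6–69.0 | 49.2–73.3 |

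In the 16 v 8 rows the expected counts are equal (0.1 × 16 = 0.2 × 8 = 1.6), so the count test cannot see a doubling of the rate. A quasi-Poisson model with log scheduled visits as offset has 45.5–72.3% power for 10% v 25% at log-SD 0.7, but rejects in about 6.6% under the null at ρ = 0.1.

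**4. Infants per arm for 80% power, 10% v 25%, mean 10 visits.** Normal approximation: (1.96 + 0.84)² × (V₁ + V₂)/Δ², with (1.96 + 0.84)² = 7.85 before rounding. V₁ and V₂ are the per-infant variances in the two arms.
- Count, log-SD 0.7, ρ = 0: V₁ = 0.09 × 10 + 0.01 × 63.2 = 1.53; V₂ = 0.1875 × 10 + 0.0625 × 63.2 = 5.83; Δ = 1.5. Result: 7.85 × 7.36/2.25 = 25.7, so 26.
- Rate, same case: V = p(1−p)[ρ + (1−ρ)E(1/n)], with E(1/n) = 0.165. V₁ + V₂ = 0.2775 × 0.165 = 0.0458; Δ = 0.15. Result: 7.85 × 0.0458/0.0225 = 16.0, so 16.
- With ρ = 0.1 the same formulas give 41 by count and 25 by rate. At log-SD 0.3 they give 13 v 11 (ρ = 0) and 22 v 20 (ρ = 0.1).

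**The case against.** The case for leaving this alone has several parts.

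- **Loose wording.** Since the measure is twice called a rate, the word used in the analysis may simply mean the same thing. The tests are not mapped to outcomes, so a t-test on per-infant counts is the natural reading, not a stated one. A chi-square of cancelled against held visits would carry a denominator, though it would ignore clustering by infant. This stands as a caveat. The text still does not say which was meant, and one sentence would settle it.
- **No documented arm effect on length.** Nothing in the documents says visit mode changes when early intervention starts, and a doubling from 8 to 16 visits is an assumption. At 10 v 12 visits and log-SD 0.7 the count test rejects in only 5–6%. This stands: the distortion is conditional. It cannot be excluded either, because the timing of transition is itself a feasibility measure.
- **Small precision gain if lengths are similar.** This stands. At log-SD 0.3 it is about 4 points of power.
- **Sizing a later trial.** The primary outcome is cost, and nothing suggests a larger trial would be sized on cancellations. The infants-per-arm figures therefore show how far the variance is inflated. They do not predict a design error.
- **Partial cover.** Visit frequency by arm, if expressed per month, would show missed weekly visits. It does not separate cancellations from other gaps.
- **Post-randomisation denominator.** True, but the raw count depends on the same exposure without showing it.

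**Conclusion.** The concern holds. As written, the analysis compares a quantity different from the one the outcome section defines, and that quantity depends on time in the programme. With no arm difference in length there is no inflation of type I error (3.9–4.4% at log-SD 0.7), and the cost is precision: 12 to 18 points of power at log-SD 0.7 and about 4 at log-SD 0.3, for 10% v 25%. With a large arm difference in length, the count comparison can be badly wrong in either direction while the per-infant rate stays near 5% under equal rates. All these sizes rest on assumed rates, lengths and spread.

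The change is worth making but is not critical. Cancellations are a secondary measure in an unpowered pilot, and no a priori feasibility criterion depends on them.

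**What to change.** In the Feasibility paragraph of the Analysis section, replace the number of cancellations with cancellations divided by scheduled visits (conducted plus cancelled). Compute this per infant and compare it by randomised arm with a t-test, giving the difference and its 95% confidence interval. This is the form already used for adaptations.

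The text should also:
- say whether a visit converted to the other mode counts as cancelled, since conversions are tracked but this is left open;
- say how an infant with no scheduled visit is handled, because the proportion is then undefined;
- report scheduled visits, time in programme and converted visits by arm alongside.

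A quasi-Poisson or negative binomial model with log scheduled visits as offset is an optional sensitivity analysis.

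The cost is SAP wording and a minor extra analysis. Conducted visits and cancellations are already captured, so no new data are needed. The drawbacks are a denominator that arises after randomisation, an unweighted proportion that is noisy for infants with few scheduled visits, and slight liberality of quasi-Poisson when infants vary in their tendency to cancel.

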### ***Adaptations***

The proportion of visits conducted within the assigned group was investigated across groups using independent samples t-tests.

### ***Acceptability***

Satisfaction scores were compared across groups using independent samples t-tests.
